## 4. Statistical Analysis and Reporting

### 4.1. Introduction

Data processing, tabulation of descriptive statistics, calculation of inferential statistics, and graphical representations will be performed primarily using SAS (release 9.4 or higher).

Commercially Confidential Information If the use of other software is warranted, the final statistical methodology report will detail what software was used for what purposes.

Continuous (quantitative) variable summaries will include the number of subjects (n) with non-missing values, mean, standard deviation (SD), median, minimum, and maximum.

Categorical (qualitative) variable summaries will include the frequency and percentage of subjects who are in the particular category for each possible value. In general, the denominator for the percentage calculation will be based upon the total number of subjects in the study population, unless otherwise specified. The denominator for by-visit displays will be the number of subjects in the relevant study population with non-missing data at each visit. If there is any missing value for a categorical analysis, a “Missing” category will be displayed as the last category in the table for the variable.

For weight, height, CCI one decimal place will be used for all summary statistics. For all other summaries, the minimum and maximum will be reported with the same degree of precision (i.e., the same number of decimal places) as the observed data. Measures of location (mean and median) and confidence interval boundaries will be reported to 1 degree of precision more than the observed data, up to 3 decimal places. Measures of spread (SD) will be reported to 2 degrees of precision more than the observed data, up to 3 decimal places.

Percentages will be presented to 1 decimal place, unless otherwise specified. Percentages equaling 0 or 100 will be displayed with no decimal places or percentage symbols.

Fractional numeric values will be presented with a zero to the left of the decimal point (for example, 0.12 – 0.30).

Unless otherwise indicated, all statistical tests will be conducted at the 0.05 significance level using 2-tailed tests, and *P* values will be reported. Corresponding 95% confidence intervals (CIs) will be presented for statistical tests, where applicable.

### 4.2. Interim Analysis and Data Monitoring

There will be no interim analyses in this study. Commercially Confidential Information

## 5. Analysis Populations

The following analysis populations are planned for this study:

- **Safety Population:** The Safety population includes all subjects who took at least 1 dose of study drug, regardless of the Protocol Amendment under which subjects were enrolled. This population will be used to summarize all safety data.

- **Full Analysis Set (FAS):** The FAS consists of subjects in the Safety Population at least one TETRAS-PS assessment Total Score at Day 7, Day 14 or early termination visit. The FAS will be used to summarize all efficacy data.

Commercially Confidential Information

- **Per-Protocol Population:** The Per-Protocol Population includes all subjects in the FAS who did not have any major protocol deviation and follow the study protocol for TETRAS-PS assessment at Day 14 or ET visit.

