## 11 STATISTICS

### 11.1 Analysis Populations

For purposes of analysis, the following populations are defined:

Safety population: All enrolled subjects who take at least 1 dose of study intervention.

- Full Analysis Set (FAS): FAS consists of subjects in the safety population who had at least 1 post-baseline assessment of both TETRAS-PS CCI . FAS will be used to summarize all efficacy data.

Commercially Confidential Information

- Exposed Population (EP): The exposed population includes all subjects in the Safety population who are at least 90% compliant with study treatment

Commercially Confidential Information

Selected efficacy analyses will be repeated in this population if this population differs from FAS.

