## 8. Efficacy Analysis

All efficacy data (including change from baseline) will be summarized and presented in tabular format and in data listings.

Efficacy variables include TETRAS-PS score, TETRAS-PS upper limb subscale score, TETRAS-PS upper limb tremor item 4 total score, Kinesia Upper Limb Tremor score,

Commercially Confidential Information

Analyses of these data will be conducted on both the FAS and Per-Protocol Population within the same output for tables; figures will only be presented on the FAS.

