## Figure 2: Planned Table Shells

Table 14.1.1  
Subject Disposition  
All Enrolled Subjects

Category	Cohort-1 (N=XX)	Cohort-2 (N=XX)	Overall (N=XX)
Enrolled	XX	XX	XX
Analysis Populations:			
Safety Population [1]	XX (XX.X%)	XX (XX.X%)	XX (XX.X%)
FAS Population [2]	XX (XX.X%)	XX (XX.X%)	XX (XX.X%)
Commercially Confidential Information	XX (XX.X%)	XX (XX.X%)	XX (XX.X%)
Per-Protocol Population [4]	XX (XX.X%)	XX (XX.X%)	XX (XX.X%)
Completed Study	XX (XX.X%)	XX (XX.X%)	XX (XX.X%)
Prematurely Discontinued from Study	XX (XX.X%)	XX (XX.X%)	XX (XX.X%)
Reason for Discontinuation:			
Adverse Event	XX (XX.X%)	XX (XX.X%)	XX (XX.X%)
Death	XX (XX.X%)	XX (XX.X%)	XX (XX.X%)
Lack of Efficacy	XX (XX.X%)	XX (XX.X%)	XX (XX.X%)
Lost to Follow-Up	XX (XX.X%)	XX (XX.X%)	XX (XX.X%)
Newly Emerged Exclusion Criteria During Study	XX (XX.X%)	XX (XX.X%)	XX (XX.X%)
Non-Compliance with Study Drug	XX (XX.X%)	XX (XX.X%)	XX (XX.X%)
Physician Decision	XX (XX.X%)	XX (XX.X%)	XX (XX.X%)
Pregnancy	XX (XX.X%)	XX (XX.X%)	XX (XX.X%)
Protocol Violation	XX (XX.X%)	XX (XX.X%)	XX (XX.X%)
Study Terminated by Sponsor	XX (XX.X%)	XX (XX.X%)	XX (XX.X%)
Withdrawal by Subject	XX (XX.X%)	XX (XX.X%)	XX (XX.X%)
Other	XX (XX.X%)	XX (XX.X%)	XX (XX.X%)

Abbreviations: ADL = activities of daily living; FAS = full analysis set; ICF = informed consent form; CCI ; PS = performance subscale; TETRAS = Tremor Research Group Essential Tremor Rating Assessment Scale.

Note: Cohort-1 is composed of subjects enrolled under the Protocol Amendment 1. Protocol Amendment 1 was finalized on 03 Dec 2018 with dosing interval of 8±2 hours during entire treatment period (Day 1-14). Cohort-2 is composed of subjects enrolled under Amendment 2 or 3. Amendment 2 was finalized on 09 May 2019 and Amendment 3 on 09 July 2019. Dosing interval was changed to 4-5 hours on Days 1, 7 and 14 in both Amendments 2 and 3.

Percentages are n/Number of subjects in the enrolled\*100.

[1] The Safety population includes all subjects who took at least 1 dose of study drug.

[2] The FAS consists of subjects in the Safety Population at least one TETRAS-PS assessment Total Score at Day 7, Day 14 or early termination visit. The FAS will be used to summarize all efficacy data.

[3] Commercially Confidential Information

[4] The Per-Protocol Population includes all subjects in the FAS who did not have any major protocol deviation and follow the study protocol for TETRAS-PS assessment.  
Personal Protected Data

Source: Listing 16.2.1.1

Table 14.1.2.1  

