Day 1, Post-dose						
n	XX	XX	XX	XX	XX	XX
Mean (SD)	XX.X (XX.XX)	XX.X (XX.XX)	XX.X (XX.XX)	XX.X (XX.XX)	XX.X (XX.XX)	XX.X (XX.XX)
Median	XX.X	XX.X	XX.X	XX.X	XX.X	XX.X
Min, Max	XX, XX	XX, XX	XX, XX	XX, XX	XX, XX	XX, XX
Change from Baseline						
n	XX	XX	XX	XX	XX	XX
Mean (SD)	XX.X (XX.XX)	XX.X (XX.XX)	XX.X (XX.XX)	XX.X (XX.XX)	XX.X (XX.XX)	XX.X (XX.XX)
Median	XX.X	XX.X	XX.X	XX.X	XX.X	XX.X
Min, Max	XX, XX	XX, XX	XX, XX	XX, XX	XX, XX	XX, XX

Abbreviations: CFB = change from baseline; ET = essential tremor; TETRAS-PS = Tremor Research Group Essential Tremor Rating Assessment Scale (TETRAS)-performance subscale (PS); SE = standard error.

Note: TETRAS-PS Total score is derived as the sum of all of the individual item scores, with the exception of item 5, only the maximum of the lower limb tremor scores will be counted. Each individual item question score ranges from 0 to 4, where higher scores indicate worse quality of life. A negative change indicates improvement.

[1] The baseline value is the last observation recorded prior to the first dose of treatment.

[2] Estimates for mean change from screening/baseline and accompanying 95% CIs and P values are from a paired t-test

[3] P-value for testing mean change from screening/baseline is based on a paired t-test with null hypothesis that the change in TETRAS-PS total score to subsequent visit is 0 with a 2-sided alternative considering a difference not equal to 0 (change in tremor).

[4] P-value for testing median change from screening/baseline is based on a Wilcoxon signed-rank test with null hypothesis that the change in TETRAS-PS total score to subsequent visit is 0 with a 2-sided alternative considering a difference not equal to 0 (change in tremor).

SOURCE: Listing 16.2.6.1.1

Table 14.2.1.1.1 (cont.)  
Summary of Central Rater TETRAS-PS Scores by Study Visit  
FAS and Per-Protocol Population

Parameter: TETRAS-PS Total Score

Study Visit Statistic	Full Analysis Set			Per-Protocol Population		
	Cohort-1 (N=XX)	Cohort-2 (N=XX)	Overall (N=XX)	Cohort-1 (N=XX)	Cohort-2 (N=XX)	Overall (N=XX)
Mean Change from Baseline (SE) [2] (95% CI for Mean Change from Baseline)	XX.X (X.XX) (XX.X, XX.X)					
P value for Mean Change from Baseline [3]	X.XXX	X.XXX	X.XXX	X.XXX	X.XXX	X.XXX
P value for Median Change from Baseline [4]	X.XXX	X.XXX	X.XXX	X.XXX	X.XXX	X.XXX
% Change from Baseline						
n	XX	XX	XX	XX	XX	XX
Mean (SD)	XX.X (XX.XX)					
Median	XX.X	XX.X	XX.X	XX.X	XX.X	XX.X
Min, Max	XX, XX					

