**Listing 16.2.2.2**  
**Inclusion and Exclusion Criteria Met/Not Met**  
**All Subjects**

Subject ID	Protocol Amendment	Date (Study Day) of: Informed Consent	All Inclusion Criteria Met?	Any Exclusion Criteria Met?
XXXXXX	X.X	DDMMYY (X)	Yes	No
XXXXXX	X.X	DDMMYY (X)	No: 05, 10	No
XXXXXX	X.X	DDMMYY (X)	No: 05	No
XXXXXX	X.X	DDMMYY (X)	Yes	Yes: 04
XXXXXX	X.X	DDMMYY (X)	Yes	No
XXXXXX	X.X	DDMMYY (X)	Yes	No

Note: Study day is calculated relative to the date of first dose of study drug (= ICF Date – Date of the first dose of date)  
Refer to Listing 16.2.2.1 for inclusion and exclusion criteria text.

***Programming note:*** If more than 1 inclusion or exclusion criterion number exists, concatenate with a comma as shown above.

Listing 16.2.2.3  
Protocol Deviations  
All Subjects

Subject ID	Protocol Amendment	Date (DDMMYYYY) (Study Day)	Event Type	Violation Level	Description
XXXXXX	X.X		XXXXXXXXXXXX XXXXXXXXXXXXXXXX	MAJOR MINOR	XXXXXXX XXXXXXXXXXXXXXXX
XXXXXX	X.X		XXXXXXXXXXXX XXXXXXXXXXXXXXXX	MINOR MINOR	XXXXXXXXXXXXXXXXXXXX XXXXXXXXXXXX
XXXXXX	X.X		XXXXXXXXXXXX	MAJOR	XXXXXXXXXXXXXXXXXXXX

Note: Study day is calculated relative to the date of first dose of study drug. For pre-dose: study day= Event Date – Date of the first dose of date;  
For post-dose: study day= Event Date – first dose date + 1.

***Programming note:*** the structure of this listing may change depending on the information in the protocol deviations file.

Listing 16.2.3  
Analysis Populations  
All Subjects

Subject ID	Protocol Amendment	Analysis Population			CCI	Primary Reason for Exclusion
		Safety [1]	FAS [2]	Exposed [3]		
XXXXXX	X.X	Yes	Yes	Yes		XXXXXXXXXXXXXXXXXX
XXXXXX	X.X	Yes	No	Yes		XXXXXXXXXXXXXXXXXX
XXXXXX	X.X	Yes	Yes	Yes		XXXXXXXXXXXXXXXXXX
XXXXXX	X.X	Yes	Yes	Yes		XXXXXXXXXXXXXXXXXX
XXXXXX	X.X	Yes	Yes	No		XXXXXXXXXXXXXXXXXXXX

Abbreviations: FAS = full analysis set; CCI ; TETRAS-PS = Tremor Research Group Essential Tremor Rating Assessment Scale (TETRAS)- CCI ; TETRAS-PS = Tremor Research Group Essential Tremor Rating Assessment Scale (TETRAS)-performance subscale (PS).

Note: All subjects received CAD-1883 300 mg BID. [1] The Safety population includes all subjects who take at least 1 dose of study drug.

[2] The FAS consists of subjects in the Safety population who had at least 1 post-baseline assessment of both TETRAS-PS CCI .

[3] Commercially Confidential Information

[4] Commercially Confidential Information

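### The SAP defines the Full Analysis Set two ways, and its Section 5 version drops subjects without a Day 7, Day 14 or early-termination TETRAS-PS total even from the tested Day 1 change

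*SAP*

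**What the plan says.** **FAS, version A.** SAP Section 5 requires "at least one TETRAS-PS assessment Total Score at Day 7, Day 14 or early termination visit". Footnote [2] of Table 14.1.1 repeats it: "The FAS consists of subjects in the Safety Population at least one TETRAS-PS assessment Total Score at Day 7, Day 14 or early termination visit".

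**FAS, version B.** Footnote [2] of Listing 16.2.3, the listing that shows each subject's population membership, reads "The FAS consists of subjects in the Safety population who had at least 1 post-baseline assessment of both TETRAS-PS CCI". Protocol Section 11.1 reads "FAS consists of subjects in the safety population who had at least 1 post-baseline assessment of both TETRAS-PS CCI". CCI marks a redaction, so version B asks for TETRAS-PS together with an assessment that the public text does not name. It does not restrict the visit.

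**Use of the FAS.** SAP Section 5 applies the FAS to all efficacy data. SAP Section 8.2.1 schedules TETRAS-PS on Day 1 and tests the change from baseline at each later visit. Table 14.2.1.1.1 has a block headed "Day 1, Post-dose", with change from baseline, confidence interval and P values. The in-clinic sensor table (14.2.5.1) uses the same populations and shell.

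**Second efficacy population.** SAP Section 8 says "Analyses of these data will be conducted on both the FAS and Per-Protocol Population within the same output for tables", and the table shells agree. The index in SAP Table 5 labels the same tables FAS/Exposed.

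**The concern.** A final SAP should give one membership rule for its main efficacy population. Here the disposition table and the population listing carry different ones, and a programmer cannot satisfy both by following the text.

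Version A also has a consequence of its own. Day 1 is a tested visit but does not qualify a subject for the FAS. Whether a subject's Day 1 change is analysed therefore depends on being rated again later. That is selection on a later event, and it applies equally to the subject's Day 1 sensor data. If the subjects lost in week 1 differ from the rest in their Day 1 response, the Day 1 estimate describes only those who were seen again.

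The Exposed versus Per-Protocol mismatch is a separate defect. It leaves open which second population fills half of each efficacy table.

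**Working it through.** The plan states no figure to reproduce: protocol Section 11.2.4 gives about 30 subjects and no power analysis, and neither document gives a dropout rate. The check is a comparison of the texts, followed by an illustration of size.

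**1. Who is in the FAS under each version?** All four subjects below are dosed and have Baseline and Day 1 TETRAS-PS totals.

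| Later course | Version A (SAP 5, Table 14.1.1) | Version B (protocol 11.1, Listing 16.2.3) |
|---|---|---|
| Rated at Day 7 or Day 14 | In | In, if the redacted measure was also done after baseline |
| Stops on Days 2–6, rated at an early termination visit | In | In, on the same condition |
| Lost in week 1, no later rating | Out | Cannot be determined |
| Later ratings all incomplete, so no total | Out | Depends on what counts as an assessment |

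Row 2 follows from protocol Section 6.2, which calls for the Day 14 procedures at an early termination visit and sets no earliest day. Row 3 can occur: protocol Section 4.4 asks only for every effort to complete that visit, and Section 4.5 treats subjects who cannot be reached as withdrawn. Row 4 follows from SAP Sections 6.1.5 and 6.1.8, which do not impute missing items.

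**2. Why row 3 is open under version B.** Protocol Section 8.1 names only TETRAS-PS on Day 1, but TETRAS-PS plus redacted text on Days 7, 14 and 21. Section 6.1.3 says that all efficacy assessments are completed on Day 1. If the redacted measure is not taken on Day 1, version B excludes the same subject. The public text does not settle this.

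**3. Size at Day 1.** Assume that all 30 subjects have Baseline and Day 1 totals and that *k* of them have no qualifying later total.

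- Share removed = *k*/30.
- 95% CI half-width for the mean change, in SD units = *t*(0.975, *n* − 1)/√*n*, with *n* = 30 − *k*.
- Shift in the Day 1 mean = (*k*/30) × (retained mean − excluded mean), so *k*/30 SD for each 1 SD of difference.

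| *k* (assumed) | *n* | Removed | Half-width (SD) | Shift per 1 SD difference |
|---|---|---|---|---|
| 0 | 30 | 0% | 0.373 | 0 |
| 1 | 29 | 3.3% | 0.380 | 0.033 SD |
| 2 | 28 | 6.7% | 0.388 | 0.067 SD |
| 3 | 27 | 10.0% | 0.396 | 0.100 SD |

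At *k* = 3 with a full 1 SD difference, the shift is 0.100/0.373, about 27% of the half-width with all 30 subjects.

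**4. Day 14.** A subject lost in week 1 without an early termination rating has no Day 14 change under any definition, so the Day 14 results stay the same.

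**The case against.** The strongest reply is that little turns on this. The visible TETRAS-PS endpoints are changes to Day 14, which do not move. The primary analysis is safety, on all dosed subjects. Day 1 is one of several tested visits in an open-label study without a power calculation. Excluded subjects' Day 1 scores still appear in the All Subjects listings. All of this stands, and it limits the weight of the point. It does not reconcile the two definitions or justify conditioning a tested Day 1 result on later attendance.

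A reader might also infer more than the text supports:

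- *Everyone who stops after Day 1 is removed.* No. An early termination rating on Days 2 to 6 qualifies.
- *The protocol and listing wording would keep a Day 1-only subject.* Not established, because that wording also needs the redacted measure.
- *The exclusion flatters the drug.* The documents give no basis for a direction. A subject who stops for intolerance could have had a larger or a smaller Day 1 response.
- *The change from the protocol was not declared.* The visible text of SAP Section 10 does not mention it, but part of that section is redacted.
- *The listing and tables will disagree on membership.* What is shown is a conflicting footnote in a shell. Nothing says that membership would be derived separately for the listing.

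**Conclusion.** The point holds in limited form. The SAP carries two FAS definitions. Under the Section 5 version, a subject with Baseline and Day 1 scores but no total at Day 7, Day 14 or early termination is left out of the tested Day 1 change and the Day 1 sensor summary. The 3 to 10% figure rests wholly on the assumed 1 to 3 of 30, and the illustrated shifts also assume a 1 SD difference that nothing in the documents supports or excludes. The Table 5 mismatch needs no assumption: the index names one second population, and SAP Section 8 and the shells name another. The edits are worth making because they cost almost nothing, not because a main conclusion is at risk.

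**What to change.** 1. In SAP Section 5, footnote [2] of Table 14.1.1 and footnote [2] of Listing 16.2.3, use one definition: *Safety subjects with a Baseline and at least one post-baseline TETRAS-PS Total Score, Day 1 included.* Apply it at every visit.
2. In SAP Section 10, state that this replaces the protocol's joint requirement for TETRAS-PS and the redacted assessment.
3. In SAP Table 5, change FAS/Exposed to FAS/Per-Protocol, or add Exposed as a further column block in the shells.

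The sensor endpoints would still depend on a TETRAS-PS rule. However, both are scheduled 2 to 4 hours after the second Day 1 dose, so a subject with a Baseline and a Day 1 total would no longer lose Day 1 sensor data through later absence.

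The cost is SAP wording, with no new data, unless Exposed is added as a column block, which also means more table output. The small downside is that *n* differs by visit, which the tables already show.

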## 6. General Considerations for Statistical Analysis

### 6.1. Statistical Definitions and Algorithms

#### 6.1.1. Baseline

The last non-missing observed value recorded on or before the date of the first dose of treatment at the Pre-dose visit will be used as the baseline observation for all calculations of change from baseline.

Wearable sensor measurements of upper limb tremor will be captured at 2 different times during the Pre-dose visit (Visit 2); the average of the 2 assessments will be used as the baseline observation for all calculations of change from baseline in wearable sensor assessments.

During the Pre-dose visit, baseline orthostatic vital signs will include 3 separate measurements, and the average of the 3 (or fewer if missing data occur) baseline orthostatic vital signs measurements will be used as baseline for comparison to all post-treatment measurements.

#### 6.1.2. Categorization of Subjects

All subjects will be categorized into the following 2 groups based on under which protocol amendment they were enrolled:

- Cohort-1: Subjects enrolled under Protocol Amendment 1.0
- Cohort-2: Subjects enrolled under Protocol Amendment 2.0 or 3.0

All analyses will be presented overall and by cohort.

Commercially Confidential Information

#### 6.1.4. Multiple Comparisons

Commercially Confidential Information

#### 6.1.5. Handling of Dropouts or Missing Data

There was no replacement for subjects who had withdrawn from the study or were lost to follow up. Individual items of TETRAS-PS, CCI, and Kinesia scores will not be imputed as described in Section 6.1.8.

#### 6.1.6. Analysis Visit Windows

Visits will be analyzed as scheduled. Unscheduled and/or repeated measurements will only be included if a scheduled measurement is not available and the unscheduled/repeated measurement falls within the analysis visit windows as described in Table 2. The windows follow the Schedule of Events in Table 1. Unscheduled/repeated measurements will be listed. Study day is defined in Section 6.1.8.

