Clinically significant abnormal laboratory or other examination (e.g., ECG) findings that are detected during the study or are present at Screening and significantly worsen during the study should be reported as AEs, as described below. The Investigator will exercise his or her medical and scientific judgment in deciding whether an abnormal laboratory finding or other abnormal assessment is clinically significant. Clinically significant abnormal laboratory values occurring during the clinical study will be followed until repeat tests return to normal, stabilize, or are no longer clinically significant. Abnormal test results that are determined to be an error should not be reported as an AE. Laboratory abnormalities or other abnormal clinical findings (e.g., ECG abnormalities) should be reported as an AE if any of the following are applicable:

- If an intervention is required as a result of the abnormality
- If action is required to be taken with the study drug as a result of the abnormality
- Based on the clinical judgment of the Investigator

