  - If the subject states that he or she is not ready to stand, the subject will be allowed to sit as positioned for one additional minute and will be asked again if they are ready to stand. The subject will proceed to stand. After standing for 2 minutes, one measurement will be taken for blood pressure and heart rate.
  - If the individual is still unable to stand, vital signs will be measured while the subject is in an upright seated position.

Orthostatic hypotension will be defined as a reduction in SBP of 20 mmHg or more, and/or a reduction in DBP of 10 mmHg or more, for the standing measurement compared to the supine or semi-supine measurement. If orthostatic hypotension is suspected, the measurement process may be repeated at the Investigator's discretion. Any confirmed orthostatic hypotension or clinically significant measurements that are associated with clinical symptoms will be recorded as adverse events.

If routine VS and orthostatic VS coincide at the same time points, the same values for routine VS (blood pressure and heart rate) during the supine or semi-supine position should be recorded in the CRFs as the same values of the start of orthostatic VS in the supine or semi-supine position.

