**Table 2: Analysis Visit Windows**

Visit Name	Visit Number	Target Start Day	Lower Limit	Upper Limit
Screening	1		-35	-14
Baseline Pre-dose	2		-14	-3
Day 1	3	1	1	1
Day 7	4	7	6	8
Day 14	5	14	13	15
Day 21	6	21	20	22

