## **9.2. Clinical Laboratory Evaluations**

Screening and safety laboratory tests will be performed at Screening, Pre-dose, Day 1, Day 7, Day 14, and at follow-up on Day 21. All laboratory test results will be summarized descriptively by study visit for the Safety Population overall and by cohort as both observed values and change from baseline values for each parameter. Categorical urinalysis results will be summarized using frequencies by study visit and cohort. Levels of composite biomarker panel for renal tubular injury will also be summarized by study visit and listed.

Shifts from baseline for clinical laboratory values below, within, or above the normal range will be provided for hematology and chemistry results by study visit. See Section 6.1.1 for the definition of baseline. Clinically significant abnormal findings will be reported as AEs. Abnormal laboratory results will be listed.

Pregnancy test results will be listed.

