#### **9.4.      Electrocardiograms**

12-lead ECGs will be obtained at Screening, Pre-dose, Day 1, Day 7, Day 14, and Day 21.

Descriptive summaries will be presented for ECG measures of PR interval, RR interval, mean heart rate, QRS interval, QT interval, and QTcF interval. Corrected QTc intervals will be calculated using Fridericia's correction formula. These summaries will be presented by study visit for the Safety Population overall and by cohort. The mean change from baseline (pre-dose) for each parameter will be plotted by study visit. Values outside the normal range will be flagged in the listings.

The number and percentage of subjects with normal, abnormal but not clinically significant, and abnormal and clinically significant ECG results will be summarized for the Safety population by study visit.

Additionally, QTcF data will be summarized by the following categories by study visit:

- QTcF > 450 msec to  $\leq$  480 msec
- QTcF > 480 msec
- QTcF > 500 msec
- Change from baseline > 30 msec to  $\leq$  60 msec
- Change from baseline > 60 msec

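### Threshold crossings seen only on a repeat or between-visit reading are listed but not counted in the QTcF, orthostatic hypotension and laboratory shift tables

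*SAP*

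**What the plan says.** SAP 6.1.6 stands under the general considerations, so it governs safety as well as efficacy data. Visits are analysed as scheduled, and an extra reading must meet two conditions to enter an analysis:

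- First condition: "Unscheduled and/or repeated measurements will only be included if a scheduled measurement is not available".
- Second condition: its study day must lie inside one of the Table 2 windows.

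For the rest, "Unscheduled/repeated measurements will be listed". SAP 6.1.9 adds that data not analysed under the plan stay out of tables and graphs.

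The visible text of SAP 9.2 to 9.4 makes no exception for safety. In SAP 9.4, "QTcF data will be summarized by the following categories by study visit". In SAP 9.2, the laboratory shifts "will be provided for hematology and chemistry results by study visit". Table 14.3.6.1.6 gives orthostatic hypotension at Baseline, Day 7, Day 14 and Day 21.

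The protocol expects some repeats. Protocol 7.10 says: "If orthostatic hypotension is suspected, the measurement process may be repeated". Protocol 7.1 says: "Clinically significant abnormal laboratory values occurring during the clinical study will be followed until repeat tests return to normal".

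**The concern.** A scheduled-only rule suits by-visit means, because it stops subjects with many readings from weighing more than others. Outlier and shift tables serve a different purpose: they tell the reader how many subjects crossed a fixed limit, whatever the investigator thought of it. If such a table can draw only on the scheduled reading, it may show fewer subjects than the data contain.

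Safety and tolerability are the primary objective and enrolment is about 30. For rare categories such as QTcF above 500 msec or an increase above 60 msec, the reader mainly takes away whether the count is none or one.

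A second gap has a different cause. Because the shells are by visit with no any-time row, they do not give the number of subjects who ever crossed a limit, even from scheduled readings alone.

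**Working it through.** The plan states no figure on this point, and the sample size rests on no power calculation, so there is nothing to reproduce.

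**1. Days covered.** The post-dose windows in SAP Table 2 are Day 1 (1 to 1), Day 7 (6 to 8), Day 14 (13 to 15) and Day 21 (20 to 22).

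- Covered: 1 + 3 + 3 + 3 = 10 of Days 1-22.
- Not covered: 22 − 10 = 12 days (Days 2-5, 9-12, 16-19); 12/22 = 55%.
- Within treatment Days 1-14: 14 − (1 + 3 + 2) = 8 days not covered; 8/14 = 57%.

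These are shares of days, not of data. All 12 are at-home days in the Schedule of Assessments.

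**2. What happens to an extra reading under 6.1.6.**

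- In a window, scheduled value missing: tabulated.
- In a window, scheduled value present: listed only, even if the extra reading is worse.
- On one of the 12 days: listed only, even if the nearest scheduled value is missing.

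**3. Whether another row picks it up.** The visible shells of Tables 14.3.6.2.3 (QTcF), 14.3.6.1.6 (orthostatic hypotension), 14.3.5.1.2 and 14.3.5.2.2 (laboratory shifts) have visit rows only. The orthostatic hypotension and laboratory shift shells also show no Day 1 row, although both kinds of measurement are taken after dosing on Day 1. By contrast, SAP 9.5.3 counts a C-SSRS Yes at any point, so the plan already uses any-time counting elsewhere. Protocol 11.2.1 plans QTcF category frequencies without tying them to scheduled visits.

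**4. Why by-visit counts do not add up.** Suppose a category shows one subject at Day 7 and one at Day 14. That may be one subject twice (1/30 = 3.3%) or two subjects (2/30 = 6.7%). The table cannot tell them apart. This holds for scheduled data too, so it comes from the shells and not from 6.1.6.

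**5. Weight of one subject.** Assume 30 treated and x subjects whose only crossing is on an uncounted reading. Exact (Clopper-Pearson) 95% limits are the 0.025 quantile of Beta(x, n − x + 1) and the 0.975 quantile of Beta(x + 1, n − x). For x = 0 the lower limit is 0 and the upper is 1 − 0.025^(1/30) = 11.6%.

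| x | Table as planned | With an any-time row | Exact 95% limits, any-time row |
|---|---|---|---|
| 0 | 0/30 | 0/30 (0%) | 0 to 11.6% |
| 1 | 0/30 | 1/30 (3.3%) | 0.1 to 17.2% |
| 2 | 0/30 | 2/30 (6.7%) | 0.8 to 22.1% |

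The documents do not give x. The visible safety sections plan no confidence interval on these proportions, so the limits show scale and are not a planned output.

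**The case against.** A reader might infer that 6.1.6 keeps extra readings out of every table, or that the safety tables drop the very readings taken because something looked wrong. The documents do not support either.

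- The primary endpoint is TEAE occurrence and severity. AE tables count by onset after first dose, not by visit window.
- Table 14.3.4.1 is a subject-level display of abnormal laboratory results and may show unscheduled values.
- If an abnormal scheduled reading prompts a repeat, the scheduled reading stays in its table. Repeats under Protocol 7.1 are largely follow-up to recovery. What goes uncounted is a worse repeat, or a crossing seen only between visits.
- Protocol 7.8 sets fixed ECG times and has no visible provision for triggered ECGs, so an unscheduled QTcF outlier is possible but not something the plan foresees.
- A subject who withdraws should have the Day 14 procedures at an Early Termination visit, and SAP 6.1.8 uses that value for change from baseline to Day 14.
- With about 30 subjects in one arm, every listed value can be read.

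All of this stands, and it limits the point. It does not remove it. A listing gives no count or denominator. Under Protocol 7.1 an abnormal laboratory or ECG finding becomes an AE through intervention, action on study drug or clinical judgment, so a crossing judged not clinically significant need not reach the AE tables. Table 14.3.4.1 carries no counts and covers laboratory data only.

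Text is also redacted in SAP 9.3, after 9.5.3, at the end of the safety table list, and in Sections 10 and 11. An exception or an any-time summary could be there.

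**Conclusion.** The point holds for the by-visit QTcF category, orthostatic hypotension and laboratory shift tables. Followed as written, the visible plan can undercount subjects who crossed a limit, for two separate reasons: the inclusion rule in 6.1.6, and shells without an any-time row. No data are lost, and the primary TEAE analysis does not use the windows.

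The size is unknown. Each uncounted subject moves a category by 1/30 = 3.3 percentage points if 30 are treated; the number of such subjects is an assumption and may be zero. The conclusion also assumes that no redacted text provides an exception. It is an inexpensive improvement that should be made, not a flaw that undermines the trial.

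**What to change.** Keep 6.1.6 for by-visit summaries, and state there that it does not apply to a new 'Any post-dose' block. That block counts each subject once over all scheduled, repeat and unscheduled readings from first dose to last visit:

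- **Table 14.3.6.2.3:** classify by the maximum QTcF and by the maximum increase from baseline. Say whether the maximum is over single tracings or triplicate means, since Protocol 7.8 takes triplicates and SAP 9.4 does not visibly say how they are combined.
- **Table 14.3.6.1.6:** count any standing-versus-supine drop that meets the SAP definition.
- **Tables 14.3.5.1.2 and 14.3.5.2.2:** give separate rows for shift to any Low and shift to any High, so that a subject may appear in both. A single worst value is undefined in a Low/Normal/High shell.

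The cost is a short addition to 6.1.6, one block in each of four shells and the direction rule for laboratory shifts. The data are already collected and listed. The small downside is that subjects with more readings have more chances to cross a limit; a footnote should say so.
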